This can include prevention, diagnostic or therapeutic interventions (e.g., drug or device) or educational, health services or basic science interventions (e.g., educational program, health care delivery model, or examining basic physiology)

Behavioral lifestyle intervention: Participants (N=40) will be randomized to the mHealth+ group Intervention group (Group A; n=20) and mHealth+ individual intervention group (Group B; n=20) group using a block randomization table. (1) The mHealth+ group Intervention group (Group A) will receive a modified Look AHEAD behavior lifestyle intervention with smartphone-based self-monitoring of diet and physical activity. This comprises ten group sessions for lifestyle intervention in 6-months. The group will receive three weekly classes in the first month and then bi-weekly classes for month 2-3, and three monthly session in month four, five, and six. The frequency and layout of these classes will allow participants to master new skills gradually, then eventually wean off, and adopt the modified lifestyle as the part of their daily lives. (2) The mHealth+ individual intervention group (Group B) will receive an abbreviated behavior lifestyle intervention with smartphone-based self-monitoring of diet and physical activity in one face-to-face individual session at the beginning of the study. In addition, participants will receive self-study materials, from Look Ahead modules, and a monthly follow-up phone calls for the duration of the study (6-months). The goal for these follow up phone calls are to assess understanding of the modules, to promote continued engagement with the study material, and to provide clarification on materials as needed. Participants in the mHealth+ group Intervention group (Group A) and mHealth+ individual intervention group (Group B will receive instruction on how to download an app to help them record their diet and physical activity at the beginning of the study. (see updates to study protocol dated below)

Fitbit offers a simple, easy-to-use tool for tracking food and physical activity. It helps set daily calorie budget, and set and work towards goals for nutrient intake, weight loss, exercise, and more. https://www.fitbit.com/inspire

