10.1. Measures to Minimize Bias: Randomization and Blinding

This section should contain a description of randomization and blinding procedures (if applicable to the study design). It should include a description or a table that describes how study participants will be assigned to study groups, without being so specific that blinding or randomization might be compromised. Plans for the maintenance of trial randomization codes and appropriate blinding for the study should be discussed. The timing and procedures for planned and unplanned breaking of randomization codes should be included. Include a statement regarding when unblinding may occur and who may unblind. Provide the criteria for breaking the study blind or participant code. Discuss the circumstances in which the blind would be broken for an individual or for all participants (e.g., for serious adverse evets (SAEs)). Indicate to whom the intentional and unintentional breaking of the blind should be reported.

The PI will not be blinded by the study mHealth+ group Intervention group and mHealth+ individual intervention group.

Participants (N=40) be randomized into two groups using a block randomization table to receive behavioral lifestyle educational intervention. Everyone will receive a baseline and end of study visits.

We divided our future participants into 4 groups (10 - (group A):10- (group A):10- (individual B):10 (individual B) and with the help of computer generated program, we will start our intervention group (Group A - n=20) first followed by our control group (Group B - n=20). (see updates dated below)

Participant in mHealth + group intervention (Group A) you will receive a total of 10 group sessions in 6-months. The group will receive 3 weekly classes in the first month and then bi-weekly classes for month 2-3, and three monthly session in month four, five, and six.

10.20.2020: we completed up to three face to face group intervention sessions (Group A) over WebEx due to COVID-19 restrictions.

10.20.20: we finished our participants (N=20) in the group intervention and due to COVID-19 restrictions we were not able to enroll our participants for the control group.

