12.1. Statistical Hypotheses

State the formal and testable null and alternative hypotheses for primary and key secondary endpoints, specifying the type of comparison (e.g., superiority, equivalence or non-inferiority, dose response) and time period for which each endpoint will be analyzed.

Behavioral lifestyle interventions using a smartphone for self-monitoring to improve frailty measurements, body weight, and glycemic control in overweight/obese older adults with T2D.

8

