12.4. Statistical Analyses

Include analysis of primary efficacy endpoints, secondary endpoints, safety analyses, and any planned interim analyses

The impact of the intervention on frailty status (non-frail, pre-frail, frail) and frailty score (0, 1, 2, 3, 4, or 5) over the 6month period (from baseline to follow-up) will be assessed by proportional odds cumulative logit (POCL) model to assess the log-odds of frailty as an indicator of being exposed to the intervention. The initial POCL model will adjust only for the baseline value of frailty status. A subsequent model will adjust for baseline age, sex, ethnic group, BMI, and Hba1c, to determine potential covariate interactions with the intervention. Continuous secondary outcomes including fasting glucose, Hba1c, and BMI will be assessed using linear regression with intervention, baseline frailty, sex, and ethnic group as categorical predictor variables and baseline age, BMI, and Hba1c as continuous predictor variables. The categorical outcomes SPPB and PROMIS scores will also be evaluated using the POCL model. Because the POCL model is complex and this is a pilot study, it is not practical or feasible to do a power analysis for the given experimental design but based on the work of Drs. [name] and [name], we believe at least 20 participants in the group (mHealth+ group Intervention group) are needed. The effect of the intervention on the change in frailty category and/or frailty scores will be used to calculate power and sample size estimation for a future, larger study.

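### With Group B never enrolled, the efficacy endpoint, the intervention hypothesis and the effect meant to size the next study have no contrast behind them; the planned one compared only a fuller with an abbreviated smartphone programme

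*Combined protocol and SAP*

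**What the plan says.** Section 7 describes the two arms.

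- Planned allocation: "Participants (N=40) will be randomized to the mHealth+ group Intervention group (Group A; n=20) and mHealth+ individual intervention group (Group B; n=20").
- Group A "will receive a modified Look AHEAD behavior lifestyle intervention with smartphone-based self-monitoring of diet and physical activity", in ten group sessions over 6 months.
- Group B "will receive an abbreviated behavior lifestyle intervention with smartphone-based self-monitoring of diet and physical activity in one face-to-face individual session". In addition, "participants will receive self-study materials, from Look Ahead modules, and a monthly follow-up phone calls for the duration of the study (6-months").
- Participants in both arms "will receive instruction on how to download an app to help them record their diet and physical activity at the beginning of the study".

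Section 10.1 treats Group B as the control: "we will start our intervention group (Group A - n=20) first followed by our control group (Group B - n=20"). The 10.20.20 entries in sections 7 and 10.1 record that Group A (N=20) finished, that Group B was not enrolled because of COVID-19, and that the investigators consider the aim still met.

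The form carries that same amendment date, but these parts do not reflect the change:

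- Section 3.1 states a feasibility objective, while the endpoint in 3.2 is first information on the efficacy of a smartphone lifestyle intervention for frailty.
- Section 12.1 gives as its whole hypothesis "Behavioral lifestyle interventions using a smartphone for self-monitoring to improve frailty measurements, body weight, and glycemic control in overweight/obese older adults with T2D", with no comparator, null or alternative.
- Sections 12.3 and 12.4 specify a proportional odds cumulative logit (POCL) model "to assess the log-odds of frailty as an indicator of being exposed to the intervention", and linear regressions with intervention as a predictor.
- Sections 12.2 and 12.4 use the effect of the intervention on frailty to plan a larger study.

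**The concern.** The endpoint and hypothesis ask whether a smartphone-supported lifestyle programme improves frailty. Answering that needs people who did not receive such a programme, and neither planned arm supplies them. With both arms enrolled, the design would have answered a narrower question: how much better the fuller package does than the abbreviated one. With one arm it answers neither question.

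Two things are at stake. First, a report that follows 3.2 as written would present Group A's before-after change as efficacy. Second, that change is the only effect now available for planning. A larger trial sized on it would be too small if its comparator shares part of the benefit, or if part of the change would have occurred without the programme.

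**Working it through.** **Plan's own figure.** The plan gives 20 per arm (40 in total) without alpha, power, effect size or variance, and 12.2 declines a power analysis. There is no calculation to reproduce. The checks below concern what can be estimated. Every effect size, alpha and drift in them is assumed.

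**1. Two arms as planned.** Take the linear model of 12.4: intercept, intervention, baseline frailty (two indicators), sex, ethnic group (one indicator, assuming two categories), age, BMI and HbA1c. That is 9 columns. With 20 in each arm and simulated covariates the rank is 9, so the A-minus-B coefficient exists. An indicator for receiving any smartphone lifestyle programme equals 1 for all 40 participants. Beside the intercept it gives rank 1 from 2 columns, so the effect against no programme is not estimable.

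**2. Group A only.** The intervention column is 1 for all 20, and the rank falls to 8 of 9. The POCL model fails in the same way. In logit P(Y ≤ j) = α_j − βx − γ·baseline with x = 1 throughout, only α_j − β is identified, so β has no estimate. Reading x as follow-up versus baseline does not rescue the model, because baseline frailty is already a covariate. A model rebuilt that way would estimate change over time, which step 3 addresses.

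**3. Group A's change as evidence of efficacy.** Suppose the programme does nothing, but participants drift by s SDs of the change score for other reasons. A two-sided paired t-test at 0.05 with n = 20 has noncentrality s√20 on 19 degrees of freedom.

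| Drift s (assumed) | Chance of p < 0.05 with no programme effect |
|---|---|
| 0 | 5% |
| 0.2 | 14% |
| 0.3 | 25% |
| 0.5 | 57% |

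The documents give reasons to expect such influences. Up to three group sessions moved to WebEx (10.1). For eight participants the in-person frailty assessment was put off until distancing ended (section 7). A focus-group question on the effect of the pandemic was added (8.6).

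**4. Carrying the effect forward.** Let D be Group A's true standardised effect against no programme, and f the fraction of it that Group B's format would also achieve. A versus B then estimates (1 − f)D, and the required sample size scales by 1/(1 − f)². For f = 0.25, 0.5 and 0.75 this is 1/0.5625 = 1.78, 1/0.25 = 4 and 1/0.0625 = 16.

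For an assumed D = 0.8 and two-sided alpha 0.05, with the normal approximation:

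- n per arm for 80% power = 2(1.96 + 0.8416)²/[(1 − f)D]² = 15.70/[(1 − f)D]²
- power with 20 per arm = Φ((1 − f)D√10 − 1.96)

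| f (assumed) | Contrast (SD) | n per arm, 80% power | Power with 20 per arm |
|---|---|---|---|
| 0 | 0.8 | 25 | 72% |
| 0.25 | 0.6 | 44 | 48% |
| 0.5 | 0.4 | 99 | 24% |
| 0.75 | 0.2 | 393 | 9% |

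The contrast detectable with 80% power at 20 per arm is 2.8016 × √(2/20) = 0.89 SD.

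**The case against.** The strongest defence has four parts.

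- **The comparator was legitimate and disclosed.** Both arms are named mHealth+, and section 7 says both use the app. A reader might infer that A versus B could not have shown efficacy at all. The documents do not support that. Superiority of the fuller programme would be evidence that it works, and a lower bound on its effect, provided Group B's programme is no worse than nothing. This stands.
- **The protocol does not claim to isolate the smartphone.** The background presents the lifestyle programme as the intervention and mHealth as a self-monitoring tool within it. This stands, so the point is not that the authors credit the smartphone. Nor do the arms differ only by group sessions: they also differ in content and dose, and self-study materials and monthly calls are described only for Group B.
- **This is a pilot with a feasibility objective.** Section 3.1 says so, the background speaks of preliminary efficacy, and 12.1 never uses the word efficacy. Group A can inform feasibility. This stands and shapes the remedy, but it does not remove the efficacy wording of 3.2 or the intervention term in 12.3 and 12.4.
- **The multipliers rest on an unsourced f and an unnamed future comparator.** This is correct. They illustrate a planning risk and do not measure an error in this protocol.

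**Conclusion.** The point holds as a mismatch between what the amended text promises and what one arm can supply. The planned contrast would have measured a net difference between two packages, with low sensitivity at 20 per arm. Once Group B was dropped, the planned intervention coefficient ceased to exist. That follows from the design and rests on no assumed figure.

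A reader might take Group A's change as the effect of the whole programme. The documents do not support that either, because nothing in the design separates the programme from time trend, regression to the mean and pandemic disruption. How large those influences are is unknown; the drift table shows only that moderate ones would be enough to mislead.

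The sample-size range of 1.8 to 16 times applies only if the next study uses the individual mHealth+ format as comparator and f lies between 0.25 and 0.75. It also supposes that Group A's effect is known, which its uncontrolled change does not establish. Feasibility remains a question that the completed arm can address.

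**What to change.** 1. Restate 3.2 and 12.1 as feasibility, matching 3.1, plus descriptive change from baseline to 6 months in Group A, with confidence intervals.
2. Say there that this change is not an estimate of efficacy, that it includes time trend, regression to the mean and COVID-19 disruption, and that it isolates neither the smartphone nor group delivery.
3. In 12.3 and 12.4, replace the models containing an intervention term with that within-group description.
4. In 12.2 and 12.4, name the comparator of the future study and do not use Group A's change as its between-arm difference. If the comparator is the individual mHealth+ format, show sample size over a range of f, for example 0.25 to 0.75, labelled as an assumption.
5. Leave the dated amendment entries unchanged, since they record what happened.

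The cost is wording in sections 3 and 12 and one small table; no new data are needed. The price is a weaker headline claim and a larger projected next study.

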8.2. Devices

N/A

8.3. Biologics

N/A

8.4. Laboratory Tests

Laboratory tests: Complete blood count, chemistry with liver function tests, lipid profile, HbA1c, and inflammatory markers (CRP, IL6) will be collected from all participants. Approximately 28 ml of blood will be collected at baseline and at end of study for clinical labs and quantifying proteins of interest. Approximately 16 ml of blood will be collected in a serum separating tube and will be used for clinical lab values (complete metabolic panel, lipids and A1c). The remaining 12 ml of blood will be collected in an EDTA tube and will be used to quantifying circulating cytokines.

04.12.20: Due to COVID-19 and social distancing order, we will be adding hemoglobin Hba1c home test for our eight participants who are finishing the study on April 20, 2020. We will continue to our virtual behavioral education session and will collect other end of study assessments virtually.

8.5. Imaging Procedures

N/A

8.6. Other Research Procedures (e.g., other safety and efficacy assessments.)

Frailty assessment: We will conduct the assessment at the baseline and then at the end of the study. Frailty is defined as the presence of $\geq 3/5$ of characteristics 1) self-reported unintentional weight loss of ≥ 10 pounds in last year, 2) self-reported exhaustion, 3) low physical activity based on the Minnesota Leisure Time Physical Activity Questionnaire, 4) weak handgrip, 5) and slowness on a 10-foot walk at the usual pace. These measures have been standardized in SALSA study ^{7,21} and will be used in this study. Pre-frailty is defined as 1 or 2 of these characteristics and Non-frailty is defined as the presence of 0 characteristics. As a measure of lower extremity function, we will use the Short Physical Performance Battery (SPPB).²² All participants regardless of frailty status are eligible for study inclusion.

5

History and Physical Assessment: We will document participants' medical history regarding his/her diagnosis of T2D, length time having T2D, and use of any glucose-lowering medications and/or insulin. Height, weight, waist circumference, and vital signs (blood pressure, heart rate, temperature, and respiration) will be measured. Patient-Reported Outcomes Measurement Information System (PROMIS): PROMIS-Global Health (GH) and PROMIS-57 questionnaires, and a single-item Binge eating question will be completed by all participants at the baseline and end of study visit. In addition, all participant will complete focus group questionnaires at the end of study visit. For this study, we will recruit 20 participants for group intervention. All participants will receive a baseline and end of study visit. Participants in the group intervention will receive 10 behavioral education sessions. We will have 4-8 participants in each group intervention The focus group will be conducted at the end of study visit and procedures (session 10, visit 11) for the group intervention population. Participants will be informed in the consent and once

again before the focus group that their responses will be audio-recorded. Participants will be informed that no personally identifiable information will be discussed or recorded as part of the focus groups, and that questions will be centered on improving the program and evaluating its successes and areas for improvement. Risks of the focus groups would include discomfort answering questions and/or discomfort from participating in a group setting and breach of confidentiality. Participants do not have to answer or discuss any questions that make them uncomfortable, and that confidentiality will be protected by maintaining the audio recordings in a secure, locked location. The PI will conduct the focus group using the following questionnaires.

Focus Group Questions

As we are currently going through lifestyle changes due to the corona virus, tell me the impact of it on your day to day on self-monitoring of diet, physical activity, and diabetes management. (04.12.20)

What behavioral strategies have been most helpful to you in making the changes?

Behavioral strategies that have worked for you?

Behavioral strategies that have not work for you?

What are your plans for staying on track in the absence of these group sessions?

Since joining the program, what are the health-related benefits that you have experienced? Since joining the program, what are the appearance-related benefits that you have experienced? How would you say these benefits have influenced your quality of life?

8.7 Attach a Schedule of Activities (SOA) Excel File [Download the Template here: Schedule of Activities]	Check to indicate that the SOA Excel File is attached \rightarrow	\boxtimes
---	--	-------------

9. Preparation/Handling/ Storage/Accountability of Investigational Drug, Biologic, or Device

 \boxtimes *N/A* - *This study does not include any investigational products (e.g. drugs, devices or biologics)*

 \boxtimes N/A - An Investigator Brochure is attached

 \bowtie N/A - A Drug/Device Manual is attached

9.1. Acquisition and accountability

State how the study intervention and control product will be provided to the investigator. Describe plans about how and by whom the study intervention will be distributed, including participation of a drug repository or pharmacy, and plans for disposal of expired or return of unused product.

N/A

9.2. Formulation, Appearance, Packaging, and Labeling

Describe the formulation, appearance, packaging, and labeling of the study intervention and control product, as supplied. Information in this section can usually be obtained from the IB or the package insert, or device labeling. This section should include the name of the manufacturer of the study intervention and control product.

N/A

9.3. Product Storage and Stability

Describe storage and stability requirements (e.g., protection from light, temperature, humidity) for the study intervention and control product. For studies in which multi-dose vials are utilized, provide additional information regarding stability and expiration time after initial use (e.g., the seal is broken).

N/A

9.4. Preparation

Describe the preparation of the study intervention and control product, including any preparation required by study staff and/or study participants. Include thawing, diluting, mixing, and reconstitution/preparation instructions in this section. For devices, include any relevant assembly or use instructions.

N/A

10. Study Intervention Additional Details

10.1. Measures to Minimize Bias: Randomization and Blinding

This section should contain a description of randomization and blinding procedures (if applicable to the study design). It should include a description or a table that describes how study participants will be assigned to study groups, without being so specific that blinding or randomization might be compromised. Plans for the maintenance of trial randomization codes and appropriate blinding for the study should be discussed. The timing and procedures for planned and unplanned breaking of randomization codes should be included. Include a statement regarding when unblinding may occur and who may unblind. Provide the criteria for breaking the study blind or participant code. Discuss the circumstances in which the blind would be broken for an individual or for all participants (e.g., for serious adverse evets (SAEs)). Indicate to whom the intentional and unintentional breaking of the blind should be reported.

The PI will not be blinded by the study mHealth+ group Intervention group and mHealth+ individual intervention group.

Participants (N=40) be randomized into two groups using a block randomization table to receive behavioral lifestyle educational intervention. Everyone will receive a baseline and end of study visits.

We divided our future participants into 4 groups (10 - (group A):10- (group A):10- (individual B):10 (individual B) and with the help of computer generated program, we will start our intervention group (Group A - n=20) first followed by our control group (Group B - n=20). (see updates dated below)

Participant in mHealth + group intervention (Group A) you will receive a total of 10 group sessions in 6-months. The group will receive 3 weekly classes in the first month and then bi-weekly classes for month 2-3, and three monthly session in month four, five, and six.

10.20.2020: we completed up to three face to face group intervention sessions (Group A) over WebEx due to COVID-19 restrictions.

10.20.20: we finished our participants (N=20) in the group intervention and due to COVID-19 restrictions we were not able to enroll our participants for the control group.

After discussing with IRB person and mentors, we decided to not to enroll participants for the Group B due to highrisk for COVID-19. We were able to receive enough information from the Group A intervention participants and to finish enrolling participants for the pilot study. Modification due to Pandemic, forgoing control arm, and worked with the interventional participants still worked with the study data to meet study aim-the deviation related to COVID-19 did not impact subject rights, safety, welfare, or the overall integrity of the science of the study.

7

